We will test the effect of glucagon in the absence and presence of ethanol in a random-order crossover design. We will give each volunteer two identical injections of glucagon, one with a blood alcohol content of approximately 0 at one visit and another with a BAC of approximately 0.1 at another separate visit.

In Both Visits

- Subjects will report to the Clinical Research Center (CRC) by approximately 7:00 AM in the fasted state from 10pm the previous night. Subjects will be asked not to take any bolus insulin after 4 am, but to keep their basal insulin running.
- A urine HCG test will be performed for all female subject who are able to become pregnant. If the test is positive, the PI will inform the subject of the test result and the visit will be cancelled.

- A dipstick drug test will be performed to ensure that subjects are not under the influence of benzodiazepines or barbiturates or opiates that could synergize with ethanol to cause central nervous system depression.
- A Breathalyzer measurement will be obtained prior to the start of the visit to ensure the subject is not under the influence of alcohol.
- Two intravenous (IV) catheter lines will be placed, one in each arm. The sampling IV will be placed on the dorsal surface of the hand or the forearm. The catheters will typically be 20 gauge or smaller.
- Blood will be drawn for measurement of hemoglobin A1c, creatinine and estimated GFR, alanine aminotransferase (ALT), aspartate aminotransferase (AST), serum albumin, and free fatty acids.
- Regular human insulin will be added to the solution of 2% human serum albumin in normal saline to allow an infusion rate of 5-20 ml/hr based on the desired hourly insulin dose. Mixing of the insulin infusate will be performed by the research pharmacy and the final desired insulin concentration will be communicated to the research pharmacy in advance of the visit. The range of insulin concentrations in the infusate are expected to be from 0.2-1.2 u/ml, depending on the mean basal insulin rate of the subject.

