- The subject will remove their own insulin pump and a primed continuous insulin infusion will be started using the insulin/saline/albumin mixture. The continuous rate will be between one-fold and four-fold higher than the mean basal insulin rate of the subject with the goal to use a minimum rate of 0.02 units/kg/hour. The insulin infusion may be used to give insulin boluses if the subject is hyperglycemic at arrival to reduce the time necessary to reach steady state. Once the appropriate rate is established (with a dextrose infusion rate that is neither too low nor too high), it will remain stable throughout the experiment. For a 70 kg, 5'10" tall man with a usual basal rate of 1 u/hr, an infusion at two-fold the usual basal rate would be 17 mU/m²/min. Therefore, for a 5 ml/hr infusion 19.88 units of insulin would be added to 50 ml of saline/albumin solution (~0.4 u/ml). A bolus of insulin that is three times the subject's mean basal rate will be given at the start of the clamp to accelerate the rise of insulin levels in the blood.
- An infusion of 20% dextrose in water will be started. BG values will be measured every 5 minutes using arterialized blood measured with the StatStrip Xpress. The dextrose infusion will be adjusted so that the blood glucose is stabilized at 90 ± 5 mg/dl. If the dextrose infusion rate is less than 2 mg/kg/min or greater than 8 mg/kg/min (for the 70 kg, 5'10" tall man, 42-168 ml/hr) then the insulin infusion rate may be adjusted. Initial stabilization is expected to take less than 3 hours.
- Blood samples (5ml) will be processed for plasma for later insulin and glucagon measurement every 20 minutes throughout the experiment.

During the Ethanol Infusion Visit Only

- Once the insulin infusion rate is established and the dextrose infusion rate has been stable for 15-20 minutes with the BG in the target range, the ethanol infusion will be started.
- The ethanol loading dose will be infused over 30 minutes, followed by a maintenance infusion. The target BAC is achieved by a specific dose and rate of alcohol infusion that is computed for each subject by estimating physiological parameters that include subject's alcohol elimination rate. An established computer model will be used (10) which is physiologically based on alcohol pharmacokinetic modeling. The parameters are based on height, weight and gender.

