- We will use a breathalyzer to estimate BAC and will adjust the maintenance infusion accordingly to reach and maintain a BAC of 0.1 ± 0.01 . This is expected to take 30 to 45 minutes. Breathalyzer readings will be collected every 5 minutes until the BAC of 0.1 is reached, and then the levels will be checked every 10 minutes.
- The ethanol infusion will be continued for a maximum of up to 4 hours
- A mock ethanol infusion will be delivered during the non ethanol visits, consisting of the half-normal saline vehicle that the ethanol is normally delivered in. This will be done in order to keep the total amount of fluid infused the same. This will be started at approximately the same time, when the insulin infusion rate has been established and the dextrose infusion rate has been stable for 15-20 minutes. The computer model will run a standard profile based on the subject's height, weight and gender without any BAC measurements needed. When the computer model predicts that the BAC has reached the desired value, and the GIR remains stable for 15-20 minutes, the

injection will be given. Note that BAC measurements in the ethanol visits will modify the standard profile to achieve a true BAC of 0.1%, but the deviations from the standard profile are usually not large, so that the volume of half-normal saline delivered will be approximately the same during ethanol and non-ethanol visits.

•
In Both Visits

- Once the GIR has been stable for 15-20 min (and the BAC has been stable at 0.1 ± 0.01 for at least 10 minutes in the Ethanol Infusion Visit or the predicted BAC has been stable for at least 10 minutes in the non-ethanol visits) two baseline plasma samples will be obtained 5 minutes apart and the glucagon injection will be given.
- A bolus of 50 mcg of Lillyglucagon will be administered by subcutaneous injection using a syringe and a small gauge needle at a depth of less than 1 cm.
- In the 60 minute period after the glucagon injection, the frequency of BG checks will be increased to every 2 minutes and blood samples will be processed for plasma at every other check (every 4 minutes).

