- Height and weight
- Blood pressure
- Hemoglobin A1c
- Hemoglobin
- Creatinine and estimated GFR
- Serum Albumin
- Aspartate aminotransferase (AST)
- Alanine aminotransferase (ALT)
- Fractionated metanephrines (in subjects with history increasing the risk for a catecholamine secreting tumor)
- Free fatty acids

During the hyperinsulinemic-normoglycemic clamp:

- Venous BG measurements
- Timing and size of glucagon dose
- Insulin infusion rate
- Glucose infusion rates

- Ethanol infusion rate
- BAC according to breath alcohol meter
- BAC according to blood alcohol measurement
- Plasma insulin levels during the hyperinsulinemic-normoglycemic clamp
- Plasma glucagon levels during the hyperinsulinemic-normoglycemic clamp
- Any adverse events

VI. b. Study Endpoints

Primary endpoint analysis:

- Area over the curve for the glucose infusion rate in the hour following a subcutaneous glucagon dose (AOC_{GIR}) with a blood alcohol content of 0 vs. approximately 0.1%

Secondary endpoint analyses:

- Maximum change in GIR from baseline after glucagon injection in the presence and absence of ethanol

We will calculate means, median, percentages, standard deviations, standard errors, inter-quartile ranges, and 95% confidence intervals in descriptive analyses. We will use paired t-test for comparison of means. We will use multivariate regression models with repeated measurements to compare means and percentages while adjusting for patient demographics characteristics such as age, gender, body mass index, and body surface area.

VI. c. Power Analysis

Assuming that the standard deviation in each arm is 20% of the mean, and a within-patient correlation of 0.5, a sample size of 15 achieves 95% power to detect equivalence when the margin of equivalence is from -20% to 20% assuming the actual mean difference is zero. The significance level (α) is 0.05 using two one-sided paired t-tests. These results are based on 2000 Monte Carlo samples.

VII. Risks and Discomforts

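### The supportive regression adjusts only for traits that are fixed within a subject, so with complete pairs it repeats the paired t-test, while the pre-ethanol GIR recorded at each visit goes unused

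*Combined protocol and SAP*

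**What the plan says.** **Design and endpoints.** Section V.d (Hyperinsulinemic-normoglycemic Clamp) states: "We will test the effect of glucagon in the absence and presence of ethanol in a random-order crossover design". The primary endpoint in section VI.b is "Area over the curve for the glucose infusion rate in the hour following a subcutaneous glucagon dose", compared between alcohol levels. The secondary endpoint is the largest GIR change from baseline.

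**Analysis.** Section VI.b says "We will use paired t-test for comparison of means" and then adds repeated-measures regression "adjusting for patient demographics characteristics such as age, gender, body mass index, and body surface area". The list is illustrative, but only within demographics. No visit-level covariate and no interaction is named.

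**Where the covariates come from.** Section VI.a lists age, sex and "Height and weight" once, among the enrollment data. BMI and BSA follow from height and weight.

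**What else is recorded.** At the ethanol visit (section V.d), once the insulin rate is set and "the dextrose infusion rate has been stable for 15-20 minutes with the BG in the target range, the ethanol infusion will be started". The mock infusion has the same trigger: "when the insulin infusion rate has been established and the dextrose infusion rate has been stable for 15-20 minutes". Section VI.a lists "Glucose infusion rates" among the clamp data. Each visit therefore has a GIR plateau measured before any ethanol. Sections VI.b and VI.c do not mention it.

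**The concern.** A reader who sees an unadjusted and an adjusted comparison agree will take the second as support for the first. Here, with complete pairs, the agreement is built in, because the two analyses are the same calculation.

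The listed covariates also cannot deal with what does differ within a subject, namely the two visit days. Section V.d lets the dextrose rate lie anywhere from 2 to 8 mg/kg/min before the insulin rate may be changed, and it lets the insulin rate range from one to four times basal. Nothing requires the two visits to match. With about 15 pairs, chance differences between visit days are plausible, and a covariate that could absorb part of them is already collected. At stake is the usefulness of the supportive analysis. The validity of the primary test is not in question.

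**Working it through.** **1. The plan's own figure.** Inputs from section VI.c: SD 20% of the mean per arm, within-patient correlation 0.5, n = 15, margin ±20%, true difference 0, two one-sided paired tests at 0.05.

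- SD of the paired difference = 20 × √(2 × (1 − 0.5)) = 20%.
- SE = 20/√15 = 5.164, with 14 degrees of freedom.
- Exact power is 95.8%. Monte Carlo gives 96.0% with 2,000 samples and 95.8% with 200,000. The stated 95% is reproduced.

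**2. Why the planned covariates cancel.** Write the outcome of subject i at visit k as Y_ik = μ + τE_ik + β′X_i + u_i + e_ik. E_ik is 1 at the ethanol visit and 0 at the other, X_i holds age, gender, BMI and BSA, and u_i is the subject effect. Then D_i = Y_i1 − Y_i0 = τ + e_i1 − e_i0, and X_i is gone. With complete pairs the estimate is the mean of D_i. Its SE is SD(D)/√n, provided the model's estimated between-subject variance is above zero.

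One simulated complete 15-subject crossover shows this:

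| Analysis | Ethanol effect | SE |
|---|---|---|
| Paired t-test | 1.4398 | 5.4349 |
| Mixed model, no covariates | 1.4398 | 5.4349 |
| Mixed model with age, sex, BMI, BSA | 1.4398 | 5.4349 |
| Fixed subject effects | 1.4398 | 5.4349 |

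**3. How the pre-ethanol GIR must enter.** Let W_ik be the stable GIR before the ethanol or mock infusion. The between-visit difference W_i1 − W_i0 is itself one number per subject, so as a main effect in the repeated-measures model it cancels just as age does. A second simulated complete crossover:

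| Analysis | Ethanol effect | SE |
|---|---|---|
| Paired t-test | −3.862 | 5.187 |
| Mixed model with age | −3.862 | 5.187 |
| Mixed model with the between-visit GIR difference as main effect | −3.862 | 5.187 |
| Mixed model with W_ik and its subject mean | −3.715 | 4.026 |
| D_i regressed on the uncentred W_i1 − W_i0, intercept | −3.715 | 4.026 |

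The last two are equivalent. The difference must stay uncentred, because centring it turns the intercept back into the raw mean difference.

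**4. Size of the gain.** Let r be the correlation between D_i and W_i1 − W_i0. The documents give no value, so a range is shown. The expected 90% CI half-width is t × c × SE:

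- Unadjusted: SE = 5.164, df = 14, t = 1.761.
- Adjusted: SE = 20 × √(1 − r²)/√15 × √(1 + 1/12), df = 13, t = 1.771. The last factor, 1 + 1/(n − 3), is the average cost of estimating one slope.
- c ≈ 1 − 1/(4 df) converts to the expected sample SD: 0.982 at 14 df and 0.981 at 13 df.

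| Analysis | SE | Half-width (points) |
|---|---|---|
| Unadjusted | 5.164 | 1.761 × 0.982 × 5.164 = 8.9 |
| r = 0 | 5.375 | 1.771 × 0.981 × 5.375 = 9.3 |
| r = 0.3 | 5.127 | 1.771 × 0.981 × 5.127 = 8.9 |
| r = 0.5 | 4.655 | 1.771 × 0.981 × 4.655 = 8.1 |
| r = 0.7 | 3.838 | 1.771 × 0.981 × 3.838 = 6.7 |

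Break-even lies near r = 0.3.

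**5. Where cancellation fails.** When 5 of the 15 subjects in the step 2 simulation lacked one visit, adding the demographics moved the mixed-model result from −0.83 (SE 6.95) to −0.50 (SE 6.73). In a logistic GEE for a binary outcome, adding age moved the ethanol coefficient from 0.539 to 0.550.

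**The case against.** The strongest reply is that the planned adjustment is redundant but harmless, and that the choice of a precision covariate for a supportive model is optional. It causes no bias and no inflated error rate, and it changes no conclusion. That stands.

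Three further points also carry weight:

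- **Incomplete data and percentages.** Section IV.a allows up to 35 enrolled, expects 20 to complete both visits and foresees discontinued experiments. Section VI.b neither limits the regression to complete pairs nor confines it to means. In those settings the demographics can act, so there is no case for deleting them.
- **The gain is uncertain.** Pre-ethanol GIR is partly a product of insulin titration. Also, if the area is measured from the pre-injection GIR, some day-to-day variation is already removed. The correlation could fall below 0.3.
- **No decision hangs on it.** Section VI.b attaches no equivalence test to the regression, so a narrower interval there leaves the trial's power as planned.

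None of this restores content to the adjusted comparison for the two named endpoints with complete pairs.

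A reader might infer more: that the 95% power is wrong, that the primary comparison is biased, or that the pre-ethanol covariate is sure to sharpen it. The documents support none of these. The power figure reproduces, the paired test is valid without covariates, and the correlation is not documented.

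**Conclusion.** The point holds as a low-cost improvement to a supportive analysis. For AOC_GIR and maximum GIR change, with complete pairs, a linear model and main effects only, adjusting for age, gender, BMI and BSA reproduces the paired t-test. The identity is not exact for single-visit subjects or binary outcomes. Using the pre-ethanol GIR could shorten the supportive interval by 8.9 − 8.1 = 0.8 points at r = 0.5 and by 8.9 − 6.7 = 2.2 points at r = 0.7. It would lengthen it by 9.3 − 8.9 = 0.4 points at r = 0. These sizes rest on section VI.c's SD and correlation, 15 complete pairs and an assumed r.

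**What to change.** In section VI.b:

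1. Name the unadjusted paired equivalence test as primary.
2. In the supportive regression for AOC_GIR and maximum GIR change, add each visit's own stable GIR from the 15–20 minutes before the ethanol or mock infusion starts, as the visit-level value together with its subject mean. Equivalently, regress the paired outcome difference on the uncentred paired difference in that GIR and read the ethanol effect from the intercept.
3. State two exclusions. The between-visit GIR difference is not to be a main effect in the repeated-measures model, because it cancels. The pre-injection GIR is not to be the covariate, because ethanol has been running by then and may have changed it.
4. The demographics may stay. Say that with complete pairs their main effects leave the ethanol contrast unchanged.

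Fix this wording before outcome data are seen. It needs no new data, procedure or subjects. The cost is one degree of freedom in the supportive analysis and a slightly wider interval there if r is below about 0.3.

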Appendix A.

The last revision date: December 17, 2015

Filters:

TdP Risk Category: **Drugs with known TdP risk**

Generic Name	Brand Names (Partial List)	Drug Class	Therapeutic Use	Risk Category	Route
Amiodarone	Cordarone®, Pacerone®, Nexterone®	Antiarrhythmic	Abnormal heart rhythm		oral, injection
Anagrelide	Agrylin®, Xagrid®	Phosphodiesterase 3 inhibitor	Thrombocytopenia		oral
Arsenic trioxide	Trisenox®	Anticancer	Cancer (leukemia)		injection
Astemizole (Removed from US Market)	Hismanal®	Antihistamine	Allergic rhinitis		oral
Azithromycin	Zithromax®, Zmax®	Antibiotic	Bacterial infection		oral, injection
Bepidil (Removed from US Market)	Vascor®	Antianginal	Angina Pectoris (heart pain)		oral
Chloroquine	Aralen®	Antimalarial	Malaria		oral
Chlorpromazine	Thorazine®, Largactil®, Megaphen®	Antipsychotic / Antiemetic	Schizophrenia, nausea, many others		oral, injection, suppository
Cilostazol	Pletal®	Phosphodiesterase 3 inhibitor	Intermittent claudication		oral
Ciprofloxacin	Cipro®, Cipro-XR®, Neofloxin®	Antibiotic	Bacterial infection		oral, injection
Cisapride (Removed from US Market)	Propulsid®	GI stimulant	Increase GI motility		oral
Citalopram	Celexa®, Cipramil®	Antidepressant, SSRI	Depression		oral
Clarithromycin	Biaxin®, Prevpac®	Antibiotic	Bacterial infection		oral
Cocaine	Cocaine	Local anesthetic	Anesthesia (topical)		topical
Disopyramide	Norpace®	Antiarrhythmic	Abnormal heart rhythm		oral
Dofetilide	Tikosyn®	Antiarrhythmic	Abnormal heart rhythm		oral
Domperidone (On non US Market)	Motilium®, Motilium®, Motinorm Cost®, Nomit®	Antinausea	Nausea, vomiting		oral, injection, suppository
Donepezil	Aricept®	Cholinesterase inhibitor	Dementia (Alzheimer's Disease)		oral
